5.3.1 Required Concomitant Medications

Not applicable.

5.4 Procedures for Monitoring Subject Compliance

All subjects will be administered the IP by study staff. Compliance with study protocol and procedures will be monitored on an ongoing basis by study staff.

6 IMMUNOGENICITY ASSESSMENT

6.1 Immunogenicity Analysis

To the extent possible and practicable, serum and plasma samples will be utilized to understand antibody-mediated mechanisms of protection elicited by vaccination with CHIKV VLP.

The immunogenicity analysis will be performed using a high-throughput *in vitro* infectivity assay developed by the Sponsor for assessing titers of neutralizing antibodies against CHIKV in serum samples. The assay is based on using a modified version CHIKV that expresses luciferase (CHIKV-luc) and measures the reduction of luciferase activity in infected cultures of Vero cells following treatment of virus with test serum. Using the CHIKV-luc assay, antibody neutralization titers can be determined via characterization of reductions of luciferase activity in the presence of immune serum. The quantitation of reporter gene expression, a correlate of the level of virus infection of cells, is determined by detection of luciferase in assay wells using a micro-plate luminometer. The CHIKV neutralizing antibody titre 80 (NT₈₀) is the reciprocal of the serum dilution that provides 80% protection of Vero cells from CHIKV-luc infection or an 80% reduction of luciferase activity compared to virus only control. Additionally, neutralization analyses may include fractionated antibody subtypes and/or F(ab)/F(ab)₂ products. Antibody responses, including IgM and IgG isotypes will also be assessed and quantified with a commercial anti-CHIKV ELISA test.

The IgG and IgM antibody levels specific to CHIKV on days 1, 8, 15, 22, and 57 will be assessed by ELISA. Human serum samples from each timepoint will be tested using InBios Anti-CHIKV IgM/IgG ELISA Enzyme Immunoassays. These kits are ELISAs, where a capture antibody specific for total human IgG or IgM is coated onto polystyrene plates. Human serum samples are added, and any IgG or IgM present in the sample becomes immobilized on the plate. An antigen consisting of the chikungunya virus E1/E2 glycoproteins is then added to the plate. Any anti-CHIKV E1/E2 antibodies present in the human serum samples will bind to the antigen and immobilize it to the plate. Next, a horseradish peroxidase (HRP)-conjugated anti-CHIKV E1/E2 antibody is added, which binds to any immobilized antigen in the wells. TMB (3,3',5,5'-tetramethylbenzidine) is used to develop the plate, and absorbance is read on a spectrophotometer at 450 nm. A calibrator control is included with the kit to establish a positive/negative cut-off absorbance. The reportable value, the Immune Status Ratio (ISR) value, is calculated by dividing the mean optical density (OD) of the test sample (for IgG or IgM) by the mean OD of the calibrator.

Peripheral blood mononuclear cells will be collected for analysis of cell-mediated immunity. CHIKV antigen-specific B and T cell subsets will be identified and characterized by evaluating cytokine and antibody secretion using ELISpot and flow cytometry assays. The cell mediated immune response will be linked to previously determined antibody levels to define a mechanistic model for humoral response.

7 SAFETY ASSESSMENTS AND REPORTING

7.1 Definitions

7.1.1 Adverse Event

An AE is any untoward medical occurrence in a clinical study subject administered a pharmaceutical product or intervention regardless of its causal relationship to the study treatment. An AE can therefore be any unfavorable and unintended sign (including an abnormal laboratory finding, for example), symptom, or disease temporally associated with the use of a medicinal product/intervention, whether or not considered related to the medicinal product/intervention.

Note: A diagnosis should be preferentially captured as an AE term and signs and symptoms should be captured only in the absence of a unifying diagnosis. If there are multiple diagnoses, then all diagnoses should be captured. The worsening of an existing sign, symptom or disease is also considered to be an AE. An abnormal laboratory finding deemed by the Principal Investigator as not clinically significant (NCS) will not be captured as an AE, but an abnormal laboratory finding that worsens after dosing with the study drug, from not clinically significant to clinically significant (CS), is considered an AE. Surgical procedures are not AEs. They are the action taken to treat a medical condition. Interventions that were planned prior to study entry for medical conditions that started prior to study entry but did not worsen during the clinical study are not reported as AEs.

7.1.2 Solicited Adverse Event

A solicited AE is a protocol-specified AE about which the Investigator (or designee) proactively asks the subjects about event occurrence. A reactogenicity event may be considered as a solicited AE per discretion of the Investigator (as described below in Section 7.1.2.1).

7.1.2.1 Reactogenicity

Reactogenicity (solicited systemic and injection site reactions) will be assessed by the subjects using paper memory aids. Information will be solicited on the following injection site reactions: pain, redness, and swelling. In addition, information will be solicited for AEs, on the following systemic reactions: temperature increases (oral) $\geq 38^{\circ}\text{C}$ ($\geq 100.4^{\circ}\text{F}$), chills, fatigue, headache, myalgia, arthralgia, and nausea.

If injection site or systemic reactions continue beyond seven days post-vaccination, these will be recorded in the Electronic Data Capture (EDC) as unsolicited AEs. For any type of reactogenicity persisting two weeks or more, the Investigator (or designee) will evaluate the reaction at the next scheduled visit and/or determine based on the nature and severity if a more immediate unscheduled follow-up visit is required to fully assess the reaction.

7.1.3 Unsolicited Adverse Event

An unsolicited AE is an AE that is spontaneously reported by the subject or discovered by the Investigator.

7.1.4 Adverse Event of Special Interest

New onset or worsening arthralgia that is medically attended will be included as an AESI. The occurrence of new onset or worsening arthralgia that is medically attended will be monitored throughout the study for all subjects. Medically attended visits include hospital, emergency room, urgent care clinic, or other visits to or from medical personnel.

7.1.5 Serious Adverse Event

An SAE is any untoward medical occurrence that at any dose: results in death, is life threatening, requires inpatient hospitalization or prolongation of existing hospitalization, results in persistent or significant disability/incapacity, or is a congenital anomaly or birth defect.

Important medical events which may not result in death, be life threatening, or require hospitalization may be considered a SAE when, based upon appropriate medical judgment, they may jeopardize the patient or subject and may require medical or surgical intervention to prevent one of the outcomes listed in this definition.

Note: Death is an outcome and not an event. The condition leading to death is the event. If no other information regarding the cause of death is available, the event will be considered “Unspecified AE”. Overnight stays at hospital/clinic that occurs during a study for social reasons (e.g., transportation difficulties, respite care) is not considered to be a hospitalization event.

7.1.6 Suspected Unexpected Serious Adverse Reaction

Suspected Unexpected Serious Adverse Reaction (SUSAR) is the term used to refer to an AE that occurs in a clinical study subject, which is assessed by the Sponsor and or study Investigator as being unexpected, serious and as having a reasonable possibility of a causal relationship (Section [7.1.8](#)) with the study drug.

7.1.7 Severity of Adverse Events

The Investigator will grade all AEs for severity. Adverse events listed in the Grading Scale in [Appendix II](#) will be graded according to the criteria in the table. Adverse events not listed in the Grading Scale will be graded as follows:

- **Mild (Grade 1):** No interference with activity
- **Moderate (Grade 2):** Some interference with activity
- **Severe (Grade 3):** Significant; prevents daily activity

- **Potentially Life-Threatening (Grade 4):** As determined by emergency room visit or hospitalization

For the study Grading Scale see [Appendix II](#).

7.1.8 Causality of Adverse Events

The Investigator is responsible for the assessment of the causality of an AE and Sponsor's Medical Monitor will also assess SAE causality, independent of the Investigator.

The following guidelines are provided for this assessment:

- **Unrelated:** No relationship between the IP and the reported event.
- **Possibly related:** The event follows a reasonable temporal sequence from the time of administration of IP and/or follows a known response pattern to the IP but could also have been produced by other factors.
- **Probably related:** A reasonable temporal sequence of the event with administration of IP exists and based on the known response to the IP, known or previously reported adverse reactions to the IP or similar products, or in the Investigator's (or designee) clinical judgment the association of the event with the IP seems likely.

If the relationship between the AE and the IP is determined to be "possible" or "probable", the event will be considered "related" to the IP.

7.2 Eliciting Adverse Events

Adverse events reported spontaneously by the subject in response to an open question from the Principal Investigator (or designee) or revealed by observation (e.g., during physical exam) will be recorded by the Principal Investigator (or designee) on the AE eCRF. Study subjects will be provided with a 24-hour telephone number to contact study personnel in case of an untoward reaction.

7.3 Reporting Requirements for Immediately Reportable Events

7.3.1 Principal Investigator's Reporting Requirements

The following events must be reported within 24 hours of awareness by the Principal Investigator (or designee) to Sponsor's Medical Monitor and Global Pharmacovigilance Department (Global PV):

- Any SAE regardless of causal association with the IP.
- Any AESI regardless of causal association with the IP.
- Confirmed pregnancy of female subjects.

The appropriate form(s) (listed below) will be completed and sent by email to the following address:

[REDACTED]
Emergent BioSolutions Inc.

Email: [REDACTED]

Telephone (toll free): [REDACTED]

For SAE/AESI, the “Serious Adverse Event/Adverse Event of Special Interest Report Form” will be completed (abbreviated hereafter as “SAE/AESI Report Form”). The SAE/AESI Report Form is **not** the same as the AE eCRF. Supporting documentation that may be emailed to accompany the form(s) can include source documentation or medical records (e.g., discharge summary for hospitalizations, lab reports) which support a diagnosis. Participant identifiers (e.g., name, address, telephone number, social security number, medical record number, or hospital/laboratory number) must be redacted from the source documentation. All SAEs that are unexpected (e.g., adverse drug reactions) must be reported to the Institutional Review Board (IRB) by the Investigator (or designee) as required by ICH GCP E6.

If a subject becomes pregnant during a study, the Sponsor will be notified. All pregnancies where conception occurred after first exposure to the IP through the EOS visit are to be followed to outcome (e.g., delivery, spontaneous/elective/therapeutic abortion), including after the study is completed and even if the participant is withdrawn from the study. If a pregnancy results in an abnormal outcome that the reporting health care professional considers might be due to the study drug, then the guidelines for expedited reporting of serious, unexpected adverse drug reactions (SUSAR) should be followed (see Section 7.3.2).

Any pregnancy that occurs during study participation must be reported using clinical study pregnancy forms (“Pregnancy Notification Form” and “Pregnancy Follow-up Form”). To ensure subject safety, each pregnancy must be reported to the Sponsor within 24 hours of learning of its occurrence. The pregnancy must be followed up to determine outcome (including premature termination) and status of mother and child. Pregnancy complications and elective terminations for medical reasons must be reported as an AE or SAE.

Spontaneous abortions must be reported as an SAE.

Any SAE occurring in association with a pregnancy brought to the Investigator’s attention during or after the subject has completed the study and considered by the Investigator as possibly related to the study treatment, must be promptly reported to the Sponsor.

The Investigator is responsible to notify their IRB according to their policy.

7.3.2 Sponsor’s Reporting Requirements

A SUSAR is a suspected adverse reaction that is both serious and unexpected (Section 7.1.6). As specified in 21 Code of Federal Regulations (CFR) 312.32, SUSARs will be reported by

the Sponsor of the Investigational New Drug Application (IND) to the FDA and to all participating Principal Investigators in an IND safety report as soon as possible, no later than 15 calendar days after the Sponsor becomes aware of the suspected adverse reaction (21 CFR 312.32(c)(1)).

In addition, any unexpected fatal or life-threatening suspected adverse reaction will be reported to FDA no later than seven calendar days after the Sponsor's initial receipt of the information (21 CFR 312.32(c)(2)).

7.4 Reporting of Other Information - Unanticipated Problems

As outlined by the Office for Human Research Protection (OHRP), unanticipated problems must be reported to the IRB according to the requirements of 45 CFR Part 46. Unanticipated problems are considered to include any incident, experience, or outcome that meets **ALL** the following criteria:

- Unexpected (in terms of nature, severity, or frequency) given:
 - Procedures that are described in the study-related documents, such as the IRB approved research protocol and informed consent document.
 - The characteristics of the subject population being entered into the study.
- Related or possibly related to participation in the study which means there is a reasonable possibility that the incident, experience, or outcome may have been caused by the sample collection.
- Suggests that the study places subjects or others at a greater risk of harm (including physical, psychological, economic, or social harm) than was previously known or recognized.

An incidence, experience, or outcome that meets the three criteria above generally will warrant consideration of substantive changes in the study or informed consent process/document or other corrective actions to protect the safety, welfare, or rights of subjects or others. Only a small subset of AEs occurring in human subjects participating in a clinical study will meet these three criteria for an unanticipated problem. There are other types of incidents, experiences, and outcomes that occur during the conduct of clinical study that represent unanticipated problems but are not considered AEs. For example, some unanticipated problems involve social or economic harm instead of the physical or psychological harm associated with AEs. In other cases, unanticipated problems place subjects or others at increased risk of harm, but no harm occurs.

The Investigator should promptly notify the IRB when an unanticipated problem involving risks to subjects or others is identified. Also, the Investigator should notify the Sponsor of unanticipated problem(s).

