1 BACKGROUND INFORMATION

1.1 Name and Description of Investigational Product

[figure not shown]
PXVX0317 is a chikungunya virus-like particle (CHIKV VLP) vaccine. The vaccine is comprised of CHIKV VLP adsorbed on Alhydrogel 2% adjuvant (2% weight per weight [w/w]) aqueous suspension of aluminum hydroxide) and stabilized with formulation buffer, which is field-formulated as a single dose of 0.8 milliliters (mL) in a syringe to be administered intramuscularly (IM) in the deltoid muscle. For additional product information, see Section 5.1 and the PXVX0317 Investigator's Brochure (IB) (1).

The target indication for PXVX0317 vaccine is active immunization to prevent disease caused by chikungunya virus.

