11.2 Institutional Review Board (IRB)

Before the start of the study, the IB, the protocol, proposed ICF(s), subject compensation (if any), Sponsor-approved study materials and advertisements, and any other written information to be provided to the subject, will be submitted to a properly constituted IRB for review. Sponsor must receive a copy of the written approval from the IRB for all of the above applicable documents prior to recruitment of subjects into the study and shipment of IP.

The IRB must provide written approval for all amendments to any of the above documents prior to implementation of these amendments at the investigational site. The Investigator is obliged to report SAEs and AESI, as well as any unanticipated problems to the IRB in addition to other information as required by the IRB.

The names (or title, if IRB procedures prohibit publishing of names) and associated backgrounds of the members of IRB (to assist in assuring that the board membership is properly constituted and operates according to 21 CFR part 56) will be given to the Sponsor prior to the start of the study along with a signed and dated statement stating that the protocol and ICF and, where applicable, any other document listed above, have been approved by them.

All correspondence between the Investigator and the IRB will be available for review by the Sponsor (or designee), and the applicable regulatory authority(ies).

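### Protocol 7.4 ties relatedness of an unanticipated problem to sample collection alone, which leaves out the vaccine, its preparation and its administration

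*Protocol*

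**What the plan says.** Protocol 7.4 (Reporting of Other Information - Unanticipated Problems) opens its definition with "Unanticipated problems are considered to include any incident, experience, or outcome that meets" all of three listed criteria. In short, these are that the event is unexpected, that it is related to the study, and that it suggests greater risk than was known.

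The relatedness criterion begins broadly: "Related or possibly related to participation in the study which means there is a reasonable possibility". The defining clause in full then names the one cause that it recognises: "there is a reasonable possibility that the incident, experience, or outcome may have been caused by the sample collection". The section later repeats that the criteria apply jointly: "Only a small subset of AEs occurring in human subjects participating in a clinical study will meet these three criteria".

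Protocol 11.2 obliges the investigator to report SAEs and AESIs to the IRB, "as well as any unanticipated problems to the IRB in addition to other information as required by the IRB". It does not define an unanticipated problem again, so the definition in 7.4 is the only one.

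The intervention is a vaccine that is "field-formulated as a single dose of 0.8 milliliters (mL) in a syringe" (Protocol 1.1).

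**The concern.** The study does more than collect samples. Every enrolled subject is planned to receive an investigational vaccine. Protocol 5.1.7 has the site mix it from two vials and an adjuvant, with a vial-to-vial transfer and a time limit after thaw. Subjects also undergo plasmapheresis on Days 22 and 57. A definition of relatedness that names sample collection alone omits the main intervention, and a site that applies the criterion as written would find that a vaccine-caused problem fails it.

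What is at stake is external safety oversight. SAP 10.1 states that there is no safety monitoring committee, so the IRB is one of the few bodies outside the sponsor and the site that would learn of a new risk. SAEs and AESIs have their own route to it. A problem that is neither depends mainly on 7.4. The AESI category is narrow: Protocol 7.1.4 limits it to new or worsening arthralgia that is medically attended.

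**Working it through.** No figure is involved, so the check is a reading of the provisions side by side.

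**Step 1: the structure of the test.** All three criteria in 7.4 must be met. An event that fails relatedness is therefore not an unanticipated problem under that definition, whatever its standing on the other two.

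**Step 2: the content of the relatedness criterion.** The opening words would cover anything arising from participation. The clause that follows is worded as a definition, not as an example, and names sample collection only. Plasmapheresis might be thought to fall within it, because the Schedule of Events and Appendix I place it beside serum collection and blood draws. Protocol 3.3.13, however, describes it as a procedure in its own right, so the text leaves this open. The vaccine, its preparation and its injection cannot be read into the words.

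**Step 3: a wider definition elsewhere.** There is none. Protocol 11.2 uses the term without redefining it. Protocol 7.1.6 does link events to the study drug ("as having a reasonable possibility of a causal relationship"), and 7.1.8 assesses causality against the investigational product. Those sections define other concepts (a SUSAR, and the causality of an adverse event) and do not feed into 7.4.

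**Step 4: the definition applied to example problems.** These are illustrations, not events that the documents report.

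| Problem | Unexpected | Related, 7.4 as written | Related, if all study causes counted | Suggests greater risk | Other IRB route named in the protocol |
|---|---|---|---|---|---|
| Unexpected frequency of severe, non-serious vaccine reactions other than AESI | Yes | No | Yes | If so judged | Only if judged an important medical event (7.1.5), or if the IRB requires it (11.2) |
| Formulation error without harm | Yes | No | Yes | If so judged | Only if the IRB requires it (11.2); the sponsor reviews it as a deviation (9.7) |
| Unexpected vaccine-caused SAE | Yes | No | Yes | If so judged | 7.3.1 and 11.2 |
| Medically attended new arthralgia | Depends | No, if vaccine-caused | Yes | Depends | 11.2, as an AESI |
| Expected mild injection-site pain | No | No | Yes | No | Not needed |
| Unexpected injury from a blood draw | Yes | Yes | Yes | If so judged | 7.4 already applies |

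The wording changes the IRB outcome in the first two rows only. Rows three and four reach the IRB by another route. Row five fails the other two criteria on any reading. Row six is already covered.

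**Step 5: whether the first row can occur.** Protocol 7.1.7 lets Grade 4 rest on an emergency room visit, whereas the SAE definition in 7.1.5 names inpatient hospitalization. A high-grade reaction therefore need not be an SAE unless it meets another seriousness criterion or is judged an important medical event.

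**Step 6: whether the second row can occur.** Protocol 9.7 requires immediate IRB notice of deviations made to remove an immediate hazard. An accidental preparation error is not one of those. Yet 7.4 itself says that an unanticipated problem may be one in which risk rises and nobody is harmed. A harmless formulation error can fit that description and still fail the relatedness clause.

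**The case against.** The strongest reply is that nobody reading the whole of 7.4 would think vaccine problems were meant to be excluded. The section rests the duty on 45 CFR Part 46. Its lead-in is inclusive in form ("Unanticipated problems are considered to include any incident, experience, or outcome that meets"). Its first criterion looks to the procedures described in the study documents, and its third asks about risk from the study as a whole. It discusses adverse events, which 7.1.1 defines in subjects given a product or intervention. This stands as evidence of intent and makes a drafting slip the likely explanation. It does not repair the clause, because a stated definition is what site staff will apply.

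A reader might also infer that every non-serious, non-AESI problem caused by the vaccine would become reportable if the clause were widened. The documents do not support that. Such a problem would still have to be unexpected and suggest greater risk, and 7.4 itself expects few adverse events to qualify.

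A reader might further infer that 7.4 is the only path to the IRB for these problems. That too goes too far. Protocol 11.2 adds whatever else the IRB requires, and the IRB's policy is not in the documents. Protocol 7.1.5 lets important medical events count as SAEs on medical judgment. Protocol 12.2 requires IRB notice of protocol changes made to remove an immediate hazard, and 12.5 requires it for suspension or termination. Preparation errors are reviewed by the sponsor as deviations (9.7), and incorrect doses are listed (SAP 7.1), although neither of these is a report to the IRB.

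Finally, the difference between 7.4 and 7.1.6 or 7.1.8 is not a contradiction, since those sections define different things. The defect lies within 7.4: its criterion opens with participation in the study and then narrows to one procedure.

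**Conclusion.** The point holds as a wording error in an operative reporting rule. As written, 7.4 leaves the vaccine, its field preparation and its administration out of the relatedness criterion, and does not clearly include plasmapheresis.

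The consequence is limited. It reaches only problems that are caused by the vaccine or its preparation (or by plasmapheresis, if that is not sample collection), are neither SAEs nor AESIs, and also meet the other two criteria. All 25 planned subjects are to be vaccinated, but the documents give no basis for estimating how many such problems would arise. No endpoint, analysis population or immunogenicity estimate is affected.

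The conclusion assumes that the clause is applied literally. A site that follows the evident intent, or an IRB whose own policy is broader, would close the gap in practice. The documents do not support a conclusion that vaccine safety problems in general would go unreported. Priority is low, but the correction is worth making because it is almost free and the trial has no safety monitoring committee.

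**What to change.** In the second criterion of Protocol 7.4, replace "may have been caused by the sample collection" with: *may have been caused by the investigational product, its preparation or administration, plasmapheresis, sample collection, or any other study procedure*. This also settles whether plasmapheresis is covered. Sections 7.3.1 and 11.2 can stay as they are.

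The cost is one phrase in a protocol amendment and possibly a few more IRB notifications. No additional data are collected, and the SAP needs no change.
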